5.4 Withdrawal criteria

Whatever the disease status, study treatment will be discontinued in case of:

- ◆ disease progression
- ◆ patient refusal
- ◆ intolerable toxicity precluding further protocol therapy
- ◆ patient's best interest
- ◆ start of any other anti-cancer agent/modality (surgery at recurrence is allowed)
- ◆ pregnancy

Patients discontinuing therapy in the absence of progression should not receive other cancer treatment before their disease progresses, unless this is clearly not in the interest of the patient. If, after treatment discontinuation, there is additional clinical information leading the investigator to conclude that the reason for discontinuation is no longer valid (except for toxicity), the subject may resume study treatment as long as no other chemotherapy, radiotherapy, immunotherapy, NovoTTF, or other treatment with antineoplastic intent has been received, with the exception of surgical intervention that yields histology not demonstrative of tumor progression. In case of toxicity in the combination arm that is

clearly attributable to either TMZ or ABT-414, that drug can be discontinued and the other can be continued. Patients that discontinue study treatment for toxicity, patient refusal and other reasons remain 'on study' and must be followed according to the follow-up schedule for progression, survival etc unless patient specifically withdraws consent from all further data collection for the study (this decision should be clearly documented e.g in the medical notes).

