6.4.1 From end of study treatment until progressive disease

Every 8 weeks (+/- 7 days)

- Gadolinium-enhanced MRI. If PR, CR, an additional scan after 4 weeks should be done to confirm the response (as per chapter 4)

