7.1.3.1 Best overall response

Best overall response is the best response designation recorded from the date of randomization until disease progression.

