The duration of overall response (DOR) will be analyzed only for the subset of subjects who experience a complete or partial response (CR or PR). For a given subject, DOR will be defined as the number of months from the day the criteria are met for CR or PR by IRC (whichever is recorded first) to the date of progressive disease or death, whichever comes first. If a subject is still responding (i.e., has not progressed nor died after CR or PR), then the subject's data will be censored at date of the last radiological assessment.

Time to Tumor Response (TTR)

Time to tumor response is defined as the time from the date of randomization to the observation of objective response (CR or PR).

For a subject who neither respond nor progress, TTR will be censored at the subject's last tumor assessment date. For subjects who progress and never respond, TTR will be set by convention as the longest time from randomization to the last tumor assessment observed across all subjects; i.e., $\max(\text{last tumor assessment date} - \text{randomization date} + 1)$ for all subjects. The distinction in censoring rule is made here since, at the time of censoring, the

former set of subjects would still have a possibility of experiencing a response (the event of interest), while the latter set of subjects never will.

Best Overall Response Rate (BRR)

Best overall response is the best response assessed by IRC from the date of randomization until disease progression or death, whichever comes first. Subjects who did not have post-baseline assessments will be considered "not-assessed." Subjects who had only one response that required a confirmatory MRI scan, which was not performed, will also be considered not-assessed.

Objective Response Rate (ORR)

Objective response includes best overall responses – complete response (CR) and partial response (PR) – assessed by IRC per RANO criteria from the date of randomization until disease progression or death, whichever comes first. All objective responses (CR and PR) must be confirmed by repeat MRI 4 weeks later than the first time when CR or PR is identified. Any subject who did not meet CR or PR including those who did not have post-baseline radiological assessments will be considered as non-responder.

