10.5 Sensitivity Analyses

Sensitivity analyses will be conducted to evaluate the robustness of efficacy results.

PFS, ORR, BRR, duration of response will be analyzed based on assessment by local investigator per RANO criteria, as supportive of the efficacy analyses with central imaging center evaluations.

An analysis of OS will be performed by fitting a Cox regression model with treatment arm and covariates identified in the references;^{4,5} i.e., performance status, tumor location, patient age, baseline steroids, tumor size and load. Treatment will be forced in the model and covariates will be selected using a stepwise procedure. Bootstrap technique will be used to estimate the posterior probability of inclusion in the Cox model. EORTC will perform the analysis with various model selection approaches.

Modified PFS is defined as the number of months from the date of randomization until the date of first progression assessed by IRC or death without receiving post anti-cancer therapy, whichever occurs first. Subjects for whom neither death nor progression have been documented will be censored on the date of the last radiological assessment if they have no post anti-cancer therapy. If a subject has other post anti-cancer therapy prior to progression or death, the data will be censored at the date of last radiological assessment prior to or on the start date of post anti-cancer therapy.

Accounting for subjects who died or progressed immediately after 2 or more consecutive missed assessments, modified efficacy endpoint of PFS to consider the date of the earliest missed radiological assessment prior to a subject's progression or death, as a date of progression, will be analyzed using the same statistical methodology as that for the secondary PFS endpoint.

For subjects with at least one measureable disease at baseline (defined as an enhancing tumor with two perpendicular diameters ≥ 10 mm), the number and percentage of subjects with objective responses will be presented using the same statistical methodology as that for the secondary ORR endpoint.

In case more than 10% are excluded from the per-protocol population, the primary efficacy analyses (both comparisons) will be performed in the per-protocol population at two-sided alpha 5%.

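### Objective response has no cut-off at new anti-cancer therapy or on-study tumour resection, and no ORR sensitivity analysis shows what that does

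*SAP*

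**What the plan says.** **Response window.** SAP 10.2 takes objective response as CR or PR "assessed by IRC per RANO criteria from the date of randomization until disease progression or death, whichever comes first". Protocol 7.1.3.1 reads: "Best overall response is the best response designation recorded from the date of randomization until disease progression". Confirmation is mandatory: "All objective responses (CR and PR) must be confirmed by repeat MRI 4 weeks later". SAP 10.1 dates a confirmed response at the first of the two evaluations.

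**Other treatment before progression.** Protocol 5.4 tells patients who stop without progression to have no other cancer treatment until they progress, "unless this is clearly not in the interest of the patient". Its list of reasons to stop study treatment includes "start of any other anti-cancer agent/modality (surgery at recurrence is allowed"). The same section lets a patient resume study treatment after surgery whose histology does not show progression.

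**Imaging after study treatment.** Protocol 6.4.1, headed "From end of study treatment until progressive disease", keeps MRI at 8-week intervals and adds: "If PR, CR, an additional scan after 4 weeks should be done to confirm the response". Protocol 15.5 sends all scans of all patients to central review.

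**How PFS treats new therapy.** Protocol 7.1.4 states that new therapy does not censor PFS. SAP 10.5 adds Modified PFS as a sensitivity analysis: "If a subject has other post anti-cancer therapy prior to progression or death, the data will be censored". For ORR, SAP 10.5 offers only local-investigator assessment and restriction to measurable disease at baseline.

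**Status of ORR.** It is H1b and H2b in the fixed sequence (Protocol 8.2.3.6, SAP 4.6), tested by a one-sided stratified CMH test (SAP 10.3).

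**The concern.** ORR is meant to show tumour shrinkage caused by the allocated treatment. Under the written rule it measures shrinkage from that treatment plus anything given before IRC progression. Three kinds of patient are exposed:

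- those who stop for toxicity or another reason and start a new treatment under the Protocol 5.4 exception;
- those whom the investigator calls progressed but the IRC does not, since Protocol 7.1.1.4 bases treatment decisions on the local read while ORR uses the IRC;
- those resected on study before IRC progression.

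The trial is open label and the toxicity profiles differ: Protocol 1.7 reports a 27% rate of grade 3/4 ocular toxicity at 1.25 mg/kg, above the dose used here. Leaving study drug without progression could therefore differ between arms. If it does, a test in the confirmatory sequence is affected. BRR, CRR and TTR have the same gap, though they are exploratory.

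**Working it through.** **1. Is there a cut-off anywhere?** The only rule linking surgery to response is in Protocol 7.1.1, and it concerns complete resection before study entry. No rule in SAP 10.1 to 10.5 or Protocol 7.1.3 ends the response window at new therapy or on-study resection. For PFS the plan states a choice and tests the alternative; for ORR it does neither.

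**2. The plan's own design figure.** No response rate, effect or power is stated for ORR. The OS figure reproduces: Φ(√118/2 × |ln 0.54| − 1.960) = Φ(5.431 × 0.616 − 1.960) = Φ(1.387) = 91.7%, as stated. It does not depend on how ORR is defined.

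**3. Size of one misattributed response.** Planned accrual is 12 × 10 + 6 × 20 = 240, or 80 per arm at 1:1:1. One responder moves an arm's ORR by 1/80 = 1.25 points.

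**4. Effect on the ORR test (illustration; all response rates are assumptions).** Let T and C be responders in two arms of n = 80, N = 160 and p̄ = (T + C)/N. The unstratified Mantel-Haenszel statistic is z = [(T − C)/n] / √[p̄(1 − p̄)(2/n) × N/(N − 1)], rejecting above 1.960. Rejection probabilities are exact sums over two independent binomials. True ORR is equal in both arms, and the expected net extra responders are in the experimental arm only:

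| Net extra of 80 | True ORR 5% | 10% | 15% |
|---|---|---|---|
| 0 | 2.1% | 2.4% | 2.4% |
| 1 | 4.4% | 4.3% | 3.9% |
| 2 | 8.2% | 7.0% | 6.1% |
| 4 | 20.9% | 15.4% | 12.7% |

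In the other direction, 2 or 4 extra control responders cut power for a true 15% against 5% from 57% to 32% or 15%. For 20% against 5%, power falls from 85% to 64% or 42%.

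**5. Does it depend on imbalance between arms?** Write observed ORR = b + (1 − b) × s × r, with b the true ORR, s the fraction switching before IRC progression and r their response to what follows.

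| s / r in ABT-414 arm | Same s in control: b = 5%, 10% | Control s = 5%: b = 5%, 10% |
|---|---|---|
| 10% / 20% | 2.2%, 2.5% | 3.7%, 3.7% |
| 15% / 30% | 2.4%, 2.4% | 9.1%, 7.2% |
| 20% / 40% | 2.4%, 2.4% | 22.3%, 15.6% |

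With equal switching there is no inflation. The 22.3% needs 80 × 0.95 × 0.40 × (0.20 − 0.05) = 4.6 net misattributed confirmed responders in one arm. With mild imbalance (5% against 2.5% switching, 10% response) the rates are 2.4% and 2.7%.

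**The case against.** The strongest reply is that the exposed group is small and the consequence remote.

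- Other treatment before progression is ruled out by default, with one exception. Planned median PFS is 2.6 and 4.8 months, so the window is short. Protocol 5.5.1.3 provides for suspending and restarting ABT-414 after severe eye toxicity, and Protocol 5.4 lets combination-arm patients continue the other agent. This stands: nothing in the documents supports switching of 10% to 20%.
- H1b is fifth and H2b sixth in the sequence. A false ORR claim needs both arms to win on OS and PFS first. This stands, so the rates above are for ORR as a stand-alone test.
- Following patients through new therapy matches the intention-to-treat set and the main PFS rule, so it may be deliberate. This stands in part. For PFS the choice is written down and tested; for ORR it is neither.

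Some stronger readings are tempting but not supported. A reader might infer that any IRC response counts; it must be confirmed and must meet the RANO conditions on steroids, T2/FLAIR and clinical status. A reader might infer that resection readily produces responders and that the central reader would not know of it. Surgery at recurrence mostly follows progression, when the window has closed, and Protocol 15.5 says only that the reader is blinded to study treatment. Bevacizumab is described as widely used in Protocol 1.2, but it is not named as a later therapy and its single-agent activity is called limited. Duration of response is not an oversight: Protocol 7.1.3.3 ties it to the PFS rule, which is explicit.

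**Conclusion.** The gap is real: a confirmed IRC response that first appears after another treatment or an on-study resection, but before IRC progression, is credited to the randomised arm, and no planned ORR analysis shows how often this matters. A reader might infer that the ORR type I error is 4% to 22%, or that the rule favours ABT-414. The documents support neither. The number of exposed patients is not given, bias requires a difference between arms, and its direction is undetermined. It is also unstated whether scans after a local-only progression reach the IRC.

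A fair illustration is one or two net misattributed responders in one experimental arm, which takes the stand-alone one-sided rate from 2.1% to 4.4% or 8.2%. This assumes 80 per arm, a true ORR of 5% in both arms and an unstratified version of the planned test. OS, PFS and the sample size are unaffected. This is a cheap improvement.

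**What to change.** In SAP 10.2 and Protocol 7.1.3.1 to 7.1.3.2, for ORR, BRR, CRR and TTR:

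- Count a CR or PR only if its first IRC assessment is dated on or before the start of any non-protocol anti-cancer therapy or on-study tumour resection.
- Allow the 4-week confirmation scan to fall after that date if no progression has occurred, and flag those cases.
- Keep all randomised patients in the denominator, with those lacking a qualifying response as non-responders. For TTR, say which existing convention applies to a patient who reaches the cut-off without a response.
- Report the present all-scans definition as a sensitivity analysis.
- Leave the PFS and DOR rules as they are.

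The cost is wording and one extra analysis. Further anti-cancer treatment is already recorded after the end of study treatment (Protocol 6.4). That section does not cover resection while study treatment continues, so confirm that the CRF captures its date. There are two downsides. ORR may fall slightly if a late response to study drug first appears after new therapy began. ORR and PFS would also handle new therapy differently, and the SAP should say so.

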10.3 Efficacy Analyses

Statistical analyses will be performed to compare the primary and secondary endpoints described in Section 10.2 between each treatment arm (Arm 1 or Arm 2) and control (Arm 3) following the fixed sequence described in Section 4.6.

Analysis Methods for TTE Endpoints

For all TTE endpoints, differences between the treatment arms and the control arm will be assessed by a log-rank test stratified by the randomization stratification factors described in Section 4.3. The p-value obtained from the stratified log-rank test will be considered as the primary basis for determination of statistical significance for the TTE endpoints.

Kaplan-Meier (KM) estimates of the survival distribution of each TTE endpoint in Arms 1 – 3 will be estimated and plotted. Two-sided 95% CIs for the KM curves will be computed using Greenwood's formula and plotted. The median for the TTE and the probability of being event-free at 6 months, 1 year (12 months) and 2 years (24 months), and their 95% CIs will be estimated from the KM curve and its 95% CI for each treatment arm.

The hazard ratios of the two treatment arms over the control arm, adjusting for the main effects of randomization stratification factors as covariates, and their 95% CIs will be estimated using a Cox's proportional hazards model (score test).

The above-mentioned methods will be referred to as *primary survival analysis methods* for the remainder of this SAP. Analysis of the following endpoints will be performed using these primary survival analysis methods:

- Overall Survival (OS)
- Progression-Free Survival (PFS) assessed by IRC
- OS and PFS in subjects with EGFRvIII Mutation (in the Ev3M population)
- Neurological Deterioration-Free Survival (NDFS)
- OS and PFS in the subgroup of subjects with timing of relapse (< 16 weeks vs. \geq 16 weeks after the first day of the last TMZ cycle)
- Time to Tumor Response (TTR)
- Duration of Response among treatment responders (CR or PR). The time origin for calculating DOR is not the date of randomization.

Objective Response Rate (ORR)

The number and percentage of subjects with objective response will be presented by treatment arm. The objective response (CR and PR) rate will be reported with exact (binomial) two-sided 95% CI for each treatment arm.

The ORR will be compared between the treatment arms over the control arm using a one sided Cochran-Mantel-Haenszel (CMH) test, stratified by randomization stratification factors. Odds ratios will be presented with 95% CIs.

Best Overall Response Rate (BRR)

The number and percentage of subjects will be presented for each response category by treatment arm.

Complete Response Rate (CRR)

The same methodology as for analysis of objective response will be applied to complete response rate.

Corticosteroid Use

Systemic corticosteroids that were given orally or by injection, reported either in prior/concomitant medication form until 35 days after the last study drug (ABT-414/TMZ/lomustine) or tumor assessment form will be summarized. Baseline steroid use is defined as any use of systemic steroid prior to and within 14 days of randomization. Post-baseline steroid use is defined as any use of systemic steroid on or after randomization. Steroid dose will be converted to a dexamethasone equivalent dose.³

Table 3. Conversion Factor to Dexamethasone Equivalent Dose

Corticosteroids (mg)	Conversion Factor*
Cortisone	0.75/25
Hydrocortisone	0.75/20
Prednisone, Prednisolone	0.75/5
Methylprednisolone, Triamcinolone	0.75/4
Betamethasone	0.75/0.6

* Dexamethasone equivalent dose (mg) = Conversion factor x Corticosteroid dose (mg).

Baseline steroid dose is defined as the average dose prior to and within 14 days of randomization, i.e., sum of daily doses divided by the number of days treated with steroids. The following summary will be presented for each treatment arm:

- The number and percentage of subjects who are treated with steroids at baseline (yes; no; missing) and post-baseline (yes; no; missing) in a two-way table.
- For subjects with no steroids at baseline and at least one steroid at post-baseline, simple summary statistics for time (in weeks) to steroid use during the study since randomization.
- The number and percentage of subjects who are treated with average steroid dose group (mg/day) at baseline (≤ 2 ; > 2 to ≤ 4 ; > 4 to ≤ 6 ; > 6 to ≤ 8 ; > 8 to ≤ 20 ; > 20 mg/day).
- The number and percentage of subjects with objective response (CR and PR assessed by IRC per RANO criteria) and Kaplan-Meier estimates of PFS, by baseline steroid use status (yes; no; missing), respectively.

In addition, steroid dose change (sustained reduction and complete reduction) relative to baseline will be summarized. Sustained reduction of steroid dose is defined as 50% or more steroid dose reduction, relative to baseline, for 50% or more of the time on study drug (ABT-414/TMZ/lomustine). Complete reduction is defined as discontinuation of steroid use for $\geq 25\%$ of the time on study drug (ABT-414/TMZ/lomustine).

- The number and percentage of subjects with objective response status (responders; non-responders) and Kaplan-Meier estimates of PFS for subjects who have sustained steroid reduction and for subjects who have complete steroid reduction, respectively.

Quality of Life

Subject self-reported health related quality of life (HRQoL) outcomes are assessed at the baseline, Week 8 MRI visit (while on-treatment), Week 16 MRI visit (while on-treatment), and Month 6 visit (any time during the 6th and 7th month after the date of

randomization regardless of treatment or progression status) by using the QLQ-C30 version 3 (Table 4) and QLQ-BN20 (Table 5).

The main objective of HRQoL assessment is to determine the impact of ABT-414 on overall global health and HRQoL. A secondary objective is to evaluate the effect of the treatment on the remaining symptoms and functioning scales as treatment-related side effects may have a (temporary) negative influence on the health related domains of HRQoL of these subjects. The QLQ (quality of life questionnaire) comprises distinct scales, each of which represents a different aspect of QoL, and the individual questions on the QLQ are called items.

The QLQ-C30 is composed of global health status/QoL scale; five functional scales (physical, role, emotional, cognitive, and social); three symptom scales (fatigue, nausea and vomiting, and pain); and six single items (dyspnea, insomnia, appetite loss, constipation, diarrhea, and financial difficulties).

Table 4. Scoring the QLQ-C30

QLQ-C30	Item (Question) Numbers	Item Range*
Global health status/QoL		
Global health status/QoL	29, 30	6
Functional scales		
Physical functioning	1, 2, 3, 4, 5	3
Role functioning	6, 7	3
Emotional functioning	21, 22, 23, 24	3
Cognitive functioning	20, 25	3
Social functioning	26, 27	3
Symptom scales/Items		
Fatigue	10, 12, 18	3
Nausea and vomiting	14, 15	3
Pain	9, 19	3
Dyspnea	8	3
Insomnia	11	3
Appetite loss	13	3
Constipation	16	3
Diarrhea	17	3
Financial difficulties	28	

* Item range is the difference between the possible maximum and the minimum responses to individual items; most items take values from 1 to 4, giving range = 3.

Table 5. Scoring the QLQ-BN20

QLQ-BN20	Item (Question) Numbers	Item Range
Symptom scales		
Future uncertainty (FU)	1, 2, 3, 5	3
Visual disorder (VD)	6, 7, 8	3
Motor dysfunction (MD)	10, 15, 19	3
Communication deficit (CD)	11, 12, 13	3
Headaches (H)	4	3
Seizures (S)	9	3
Drowsiness (Dr)	14	3
Hair loss (HL)	16	3
Itchy skin (IS)	17	3
Weakness of legs (WL)	18	3
Bladder control (BC)	20	3

The brain cancer module (QLQ-BN20) is meant for use among brain cancer subjects varying in disease stage and treatment modality (i.e., surgery, chemotherapy, radiotherapy, etc.). It is meant to be complemented by the QLQ-C30. It is composed of 20 items forming 11 symptom scales (7 single item scales and 4 multi-item scales).

All scales and single items are reported on categorical responses, and will be linearly converted to numeric values 0 through 100. Given a scale, the raw score (RS) is computed as the mean of component items over the number of items answered for that scale. Then the scale score (SS) will be computed as following.

For global health status/QoL, and symptom scales/items,

$$SS = \{(RS - 1) / \text{range}\} \times 100.$$

For Functional scales,

$$SS = \{1 - (RS - 1) / \text{range}\} \times 100.$$

If 50% or more of the items are answered for a given scale, the scale score will be computed as described above. If not, the scale score will not be computed. For example, physical functioning contains 5 items (questions 1 through 5), and the scale score is calculated if at least 3 of the items are answered. For single-item measures (dyspnea, insomnia, appetite loss, constipation, diarrhea, and financial difficulties), none of the single-item measures can be computed if not answered. If a scale score cannot be computed, the outcome for that score is left blank.

Global health status/QoL is the primary HRQoL endpoint. The other scales from the QLQ-C30 and QLQ-BN20 will be analyzed on an exploratory basis as secondary HRQoL endpoints. The financial difficulties scale (QLQ-C30) will not be analyzed.

All QoL analyses will be performed for the subset of the ITT population for whom at least one valid post-baseline QoL form has been collected. A subject will not be included in a change from baseline analysis unless a corresponding valid QoL form at baseline has also been collected.

Compliance for a group of subjects at a certain time point T is defined as:

$$\text{Compliance (T)} = \frac{\text{Valid QoL form within [L, U]}}{\text{QoL form expected at T}}$$

Where L and U are the lower and upper bound of the time windows associated with T. The protocol schedule as specified in the protocol can be applied to this definition. The resulting values for T, L and U are summarized in [Table 6](#).

Table 6. Visit Window for QoL

	T	L	U	Window Length
Baseline	Date of randomization = D0	D0 – 1 week	D0	1 week
Week 8 (on-treatment)	Week 8 MRI visit date = D1	D1 – 1 week	D1 + 1 week	2 weeks
Week 16 (on-treatment)	Week 16 MRI visit date = D2	D2 – 1 week	D2 + 1 week	2 weeks
At 6 months	D0 + 6 months = D3	D3 – 30 days	D3 + 30 days	2 months

QoL forms are considered as invalid if either:

- All questions on the form are blank.
- The completion date is unknown or it cannot be assigned to a single assessment time point.
- The completion date falls outside all time windows.
- Multiple forms are received during the same time window. In the latter case, the form closest to the intended assessment time will be kept. In case of equidistance, the earlier form will be kept.

Forms are expected at T for each subject that was within the assessment window. A subject is considered to be within the assessment time window if at least one of the following conditions is met:

- At least one valid QoL form received within L and U
- Time on study > time from randomization till T

For the baseline assessment, all subjects are expected to have a completed QoL form.

The compliance rate between the arms will be compared at each post-baseline time point using a chi-square test. The following analyses will be presented per time-point:

- Compliance rate with QoL assessment by treatment group and overall
- Percentage of questions answered by treatment group (summary statistics)

- Comparison of compliance rates (chi-square test or fisher exact test (if expected cell frequencies are < 10))

In case significant differences are found, explanation of these differences should be sought and the analysis strategy adapted accordingly.

For each scale, the treatment group differences will be evaluated by analyzing the change from baseline to each of the three post-baseline time-points and to the final measurement (last QoL assessment per subject) using a one-way analysis of variance (ANOVA) model. Simple summary statistics for QoL assessments at each timepoint will also be presented. No adjustment for multiplicity is made since it is exploratory. For QoL assessment data, AbbVie will only perform and present simple summary statistics at each timepoint and change from baseline analysis. Other QoL data will be modeled and analyzed by EORTC.

Changes in HRQoL scores per time point will be evaluated by classifying them according to the 10 point change threshold into 3 categories:

- **Improved:** defined as a 10 point or more improvement (i.e., increase for functional scales and decrease for symptom scales) from baseline.
- **Stable:** defined as a less than 10 point change from baseline.
- **Deteriorated:** defined as a 10 point or more deterioration (i.e., decrease for functional scales and increase for symptom scales) from baseline. Subjects without a valid HRQoL outcome will be considered as having deteriorated.

In case of discrete numbers ($N < 10$), categories may be combined. The subsequent proportions will be compared between treatment arms using a chi-square test in the intent-to-treat population.

